### B1. PURPOSE OF PROTOCOL

The purpose of this randomized placebo-controlled trial is to evaluate the efficacy of postoperative oral suvorexant treatment on nighttime wakefulness after persistent sleep onset (WASO) among adult cardiac surgical patients recovering in the cardiac intensive care unit (ICU).

#### Primary objective

To evaluate the efficacy of postoperative oral suvorexant treatment on nighttime wakefulness after persistent sleep onset (WASO) among adult patients following cardiac surgery and recovering in the cardiac ICU. The primary hypothesis is that suvorexant compared with placebo decreases WASO, as measured by a specialized electroencephalogram (EEG), the SedLine monitor, during the first night in the cardiac ICU.

#### Secondary objectives

To evaluate the efficacy of postoperative oral suvorexant treatment on total sleep time (TST) as an additional measure of sleep maintenance. Secondary hypotheses are that suvorexant compared with placebo increases TST during the night of the sleep trial in the cardiac ICU.

#### Exploratory objectives

To determine the effect of postoperative oral suvorexant on postoperative delirium and delirium free days, to evaluate time to sleep onset (TSO) as a measure of sleep onset latency, and to explore patients' comorbidities, treatments, and conditions that may modify the sleep promoting effects of suvorexant in the ICU. We will test the exploratory hypotheses that:

- suvorexant compared with placebo decreases incidence of postoperative in-hospital delirium and increases delirium free days, as measured daily by the Confusion Assessment Method (CAM), CAM-ICU, and the Delirium Symptom Interview until hospital discharge (if CAM screening positive),
- suvorexant compared with placebo decreases TSO during the night of the sleep trial in the cardiac ICU,
- the effect of suvorexant will be modified by distinct perioperative factors leading to insomnia in the ICU, such as procedural severity, circadian disruption, and pharmacological treatment with centrally acting drugs.

### B2. SIGNIFICANCE AND BACKGROUND FOR THE STUDY

#### **Importance of study**

Insomnia frequently occurs in patients admitted to an intensive care unit. ICU patients are exposed to circadian desynchronization phenomena similar to the experimental condition of a "constant routine", an established technique to assess human circadian rhythmicity and characterized by constant posture, temperature, dim light and noise, and feeding stimuli. Insomnia in the ICU can also be the consequence of a systemic stress response due to procedural pain and inflammation. In addition, centrally acting drugs given during anesthesia or for postoperative pain therapy could affect postoperative sleep in patients in the ICU [1]. Our data show that under these conditions, all patients demonstrate a severe impairment of sleep architecture [2]. Thus, it can be assumed that the majority of surgical ICU patients can be characterized as suffering from insomnia. As a consequence of the impaired sleep architecture, sleep promoting agents are frequently prescribed in ICU patients. In our hospital, patients who stay in the ICU for more than 48h often receive benzodiazepines (20%) and opioids (30%) during nighttime, which reduce REM sleep and have deliriogenic effects (see *Preliminary Data* below).

#### **Background on suvorexant**

Suvorexant is a sleep-promoting orexin receptor antagonist with FDA approval for the treatment of adult insomnia. In phase 3 clinical trials, suvorexant proved superiority over placebo in both measures of impaired

sleep onset and sleep maintenance in the elderly and non-elderly, objectively measured by polysomnography. Furthermore, suvorexant improved subjective outcomes of total sleep time, sleep onset latency, and impact of impaired sleep on daytime functionality [3]. Suvorexant is well-tolerated and its side effects are minor and related to the desired end-point [4]. Similar to the suvorexant filing studies, our outcomes will include objective measures of sleep maintenance (WASO, total sleep time) and onset (sleep onset latency) [5-7]. Subjective sleep quality will be assessed using the validated Richards-Campbell Sleep Questionnaire (RCSQ) [8, 9].

### **Assessment of sleep physiology**

Due to the complex nature of sleep physiology, different methods of sleep assessment are required depending on the cohort to be studied. Questionnaires or sleep diaries are used to capture subjective quality and duration of sleep and serve as important screening tools. Objective measurements of sleep are achieved through EEG-monitoring. EEG-derived assessment of sleep differentiates wakefulness (stage 0), REM-sleep and non-REM-sleep (stages N1 to N3). Polysomnography (PSG), which combines EEG, measurement of eye movements, and electromyographic measurement of muscle activity, is considered the gold standard in determining sleep phases and diagnosing sleep disorders. A full PSG is, however, associated with discomfort and may affect the quality of sleep and the effectiveness of the sleep promoting agent, particularly in patients after surgery who are vulnerable to pain and agitation. A less invasive approach for the quantification of sleep is the SedLine® Brain Function Monitor, which consists of one disposable electrode with several sensors. Compared to polysomnography, the SedLine® Brain Function Monitor has a higher feasibility in collecting EEG measurements in challenging environments. The SedLine® monitor uses a symmetrical bilateral array of sensors that provides four-channel data. Bifrontal electrodes measure four channels of raw EEG with separate displays for locomotor EMG artifacts. The frontal electrode placements are similar to those recommended by the American Academy of Sleep Medicine [10].

A trial in subjects who underwent simultaneous PSG and SedLine monitoring demonstrated similarity of PSG and SedLine data including typical sleep architecture with an initial descent from lighter to deeper sleep stages at sleep onset, a concentration of deep sleep (stage N3) in the early portion of the night, a concentration of REM in the later portion of the night, and a number of transitions between sleep stages and awakenings that are within the normal range [11]. This group further successfully performed sleep monitoring in an ICU setting using the SedLine monitor demonstrating its feasibility and good tolerance in a similar study cohort [11].

There is some evidence suggesting that typical EEG patterns usually associated with sleep may be absent in ICU patients (atypical sleep), while EEG during behaviorally confirmed wakefulness may also be abnormal (pathological wakefulness) [12], which cannot be differentiated by conventional assessment of sleep. Recently, an EEG-derived index, the odds-ratio product (ORP) has been proposed, allowing off-line assessment of atypical sleep and pathological wakefulness [13, 14].

In addition, skin temperature recordings (which are already part of the standard operating protocol in the ICU) will provide information about patients' circadian function.

### **Delirium in the ICU**

Delirium is a syndrome of acute organ dysfunction occurring in up to 50% of ICU patients [15], which carries financial and societal burdens due to its association with increased morbidity, mortality, and prolonged hospital stays. The occurrence of ICU delirium predicts a 3 to 13-fold rise in the likelihood of death within one year after adjusting for severity of illness, coma, sedatives, and other relevant covariates [16]. Delirium is usually multifactorial, and sleep deprivation is a contributing mechanism.

It has been reported that suvorexant may have preventive effects on postoperative delirium [17]. However, the published evidence is poor, since sleep in those studies was not formally assessed using objective methods and subjective assessments failed to identify an effect of suvorexant on sleep onset or maintenance. Also, the incidence of delirium was surprisingly low in this study (< 10 percent), and no patient in the intervention group developed delirium [17]. These are surprising findings which are at odds with the sound biological concepts and results of published, carefully conducted studies. It is frankly hard to believe that suvorexant given at a dose that does not improve sleep quality eliminates delirium in the ICU. The effect of suvorexant on postoperative delirium in the intensive care unit in patients after cardiac surgery were analyzed and recently published [18]. The authors reported that following routine use of suvorexant 20 mg, only one patient out of 36 presented with postoperative delirium, as compared to 11 of 52 patients prior to the introduction of suvorexant. The small

sample size and insufficient confounder control limit the value of this study. In addition, sleep was not quantified - so as of today, it is unclear as to whether the observed, numerical reduction in postoperative delirium rate by suvorexant is the consequence of improved sleep quality.

### Assessment of delirium

In this study, delirium will be assessed daily using the Confusion Assessment Method (CAM) or CAM-ICU for reintubated patients [19]. The CAM is a standardized tool for screening purposes based on the four core features of delirium: acute onset and fluctuating course, inattention, disorganized thinking, and altered level of consciousness. The CAM is implemented into routine clinical practice at our institution. In addition, to verify the CAM screening results in CAM-positive patients we will perform the Delirium Symptom Interview, a diagnostic set of tests evaluating attention, orientation, and memory [19]. We have recently conducted and published a randomized clinical trial investigating effects of intravenous acetaminophen on postoperative delirium at our institution, which successfully utilized the same methods of outcome assessment [19]. Given the importance of insomnia and delirium in the ICU, there is a need for a well-designed study that examines the effects of suvorexant on sleep and delirium in critically ill patients. Our study will inform the effect size calculation for those future trials.

### Preliminary data

[figure not shown]
#### Sleep in the ICU

We recently studied sleep in ICU patients using polysomnography during the night after extubation. We observed a severe disruption of sleep architecture: on average, study patients slept less than 4.5 h, predominantly in non-REM sleep stage 1 and non-REM sleep stage 2. Only 10% of patients reached REM sleep. Sleep cycles were fragmented with a high number of arousals from sleep [2]. Thus, the cohort studied here meets the insomnia criteria independently of any pre-admission diagnosis of insomnia.

To estimate the need for treatment of insomnia in our institution, we analyzed the sedative medication given during nighttime at the intensive care units at BIDMC in patients who stayed in the ICU for more than 48 h during the year 2017. **Figure 1** shows that about one third and one fifth of patients receive opioids and benzodiazepines during nighttime, respectively.

#### Delirium in the ICU

Based on our study conducted in a similar cohort [19], we expect an incidence of delirium of 28.3% with an average of 20-25 delirium free days during the hospital stay. We further examined our data obtained in the cardiovascular ICU and found that the incidence of delirium was similar for patients undergoing isolated coronary artery bypass graft (44/179, 24.6%) and coronary artery bypass with aortic (8/32, 25.0%) or other (2/9, 22.2%) cardiac valve replacement surgery.

**Figure 1.** Administration of sedatives and opioids during nighttime (6 PM - 6 AM) in ICU patients admitted to Beth Israel Deaconess Medical Center (BIDMC) ICU for more than 48h in 2017.

## B3. DESCRIPTION OF RESEARCH PROTOCOL

### A. Study Design – Overview, Methods, Procedures

#### Study design & overview

- This is a single-center, randomized, double-blind, placebo-controlled trial expected to enroll 120 subjects. Participants will be enrolled preoperatively and randomized in a 1:1 ratio to receive suvorexant or placebo. Prior to randomization, informed consent will be obtained from all participants. The patient is first asked to report information about their sleep using the Richards-Campbell Sleep Questionnaire (RCSQ). Patients will be asked to complete a sleep questionnaire for at least one night before surgery or, if possible, daily, starting 3 days before surgery. The questionnaire will be performed online in RedCap; patients will be emailed a link to the survey. If patients do not have access to an internet-enabled device, they will be handed the RCSQ on paper and asked to complete it before surgery. The intervention (study drug) will be applied for 7 nights starting the night after postoperative extubation in the ICU. Primary and secondary outcomes will be assessed once during the night of the sleep trial in the ICU. The sleep trial will take place during the first night after extubation if the patient has been extubated before 7pm. If patient is extubated after 7:00 pm study medication will be administered the night after extubation only if still in ICU.

Exploratory outcomes will be assessed from day of extubation until hospital discharge. An outline of the study procedures is provided in **Figure 2**.

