#### Screening Tests

After obtaining informed consent (approach detailed in section A6), authorized members of the study team will conduct screening assessments.

1. Confusion Assessment Method (CAM): Trained assessors will administer the CAM to enrolled participants to identify those with delirium. Patients identified as CAM positive will be excluded.
2. Montreal Cognitive Assessment (MoCA): Trained assessors will administer the MoCA to enrolled participants to identify those with undiagnosed, early stage cognitive decline. Patients with a MoCA score below 23 points will be excluded. The test ranges from 0 [worst] to 30 [best], with 26 and above typically considered “normal” range.

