#### Randomization and blinding

After postoperative extubation, eligible patients will be randomly allocated in a 1:1 ratio to receive either suvorexant 20 mg or placebo. If extubation is planned outside of research pharmacy hours, randomization and drug preparation will take place in coordination with research and hospital pharmacy in accordance with their policy. Randomization will be performed by computer-generated variable block size random allocation stratified by duration of perioperative anesthesia and sedation, using a cut-off value of 420 minutes of perioperative sedation (i.e. duration of anesthesia and postoperative sedation of equal to or over 420 minutes). The allocation sequence will be provided to the research pharmacy. To achieve blinding, the study drug and placebo will be delivered in the form of non-identifiable pills, containing either the active ingredient suvorexant, or lactose. Individual patients' drug bottles will be labeled with randomization numbers. Randomization number-specific codebreakers, prepared by the research pharmacy, will contain information about a patient's treatment allocation in a sealed envelope and will be kept in the patient's study record. If unblinding procedures are necessary for clinical reasons, the clinical team will be able to contact a member of the research team with access to the codebreaker at any time by pager or phone. The codebreaker envelope is only to be opened with PI approval as instructed on the envelope. The PI will immediately inform the research pharmacy and study team of any unblinding procedures. Delivery of research medication to the patient care area will take place per pharmacy guidelines. Disposal of any unused study medication will be done per pharmacy guidelines.

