### Primary Exclusion criteria:

1. Preoperative left ventricular ejection fraction of less than 30%
2. Renal failure (creatinine >2 mg/dl or dialysis dependence)
3. Liver failure (CHILD-Pugh score > 6)
4. Coma (RASS<-1)
5. Signs and symptoms of delirium and agitation at time of enrollment (CAM-ICU positive)
6. Montreal Cognitive Assessment (MoCA) below 23 at time of consent
7. Psychiatric or neurologic diseases (including chronic benzodiazepine use, bipolar disorder, psychotic disorder, posttraumatic stress disorder, requirement of prophylactic psychiatric medication, evidence of acute depression on screening visit, preexisting cognitive impairment, Alzheimer disease, Parkinson's disease, medications for cognitive decline, history of recent seizures (within 1 year prior visit), alcoholism or documented history of alcohol abuse, and narcolepsy)
8. Severe sleep apnea requiring home CPAP treatment
9. Morbid obesity (BMI >40)
10. Known or suspected pregnancy (there are no adequate and well-controlled studies of suvorexant in pregnant women. Based on animal data, Suvorexant may cause fetal harm).
11. Patients with known hypersensitivity to study medications
12. English language limitations (Sleep assessment and delirium assessment tools are only validated in English)
13. Patients enrolled in other interventional studies which could confound the primary endpoint.

Participants who do not speak English will be excluded because of their inability to complete the cognitive assessments, which have been extensively validated in English. Adult patients unqualified or incapable of giving legal consent will be excluded. Secondary exclusion criteria after enrollment will include massive intraoperative hemorrhage, postoperative respiratory failure, loss of enteral access and signs and symptoms of delirium and agitation at time of study drug initiation (CAM ICU positive) . An overview of eligibility criteria is provided in **Figure 3**.

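### The exploratory delirium window opens on the day of extubation, before randomization and first dose, and no rule covers episodes that start and clear in that interval

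*Combined protocol and SAP*

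**What the plan says.** **Outcome window.** Study design & overview (B3.A): "Exploratory outcomes will be assessed from day of extubation until hospital discharge". Study endpoints lists delirium incidence and delirium-free days among the exploratory outcomes. The Delirium paragraph under Assessment of study endpoints covers the whole stay, ICU and ward, with a daily CAM or CAM-ICU. It sets no earliest onset time.

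**Randomization and first dose.** Randomization and blinding: "After postoperative extubation, eligible patients will be randomly allocated in a 1:1 ratio to receive either suvorexant 20 mg or placebo". Study interventions sets dosing at 9 pm, with delivery allowed until 10 pm. Study design & overview fixes the first night: "The sleep trial will take place during the first night after extubation if the patient has been extubated before 7pm", and "If patient is extubated after 7:00 pm study medication will be administered the night after extubation only if still in ICU".

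**Delirium exclusions.** There are two time points. Before surgery, Screening Tests says "Patients identified as CAM positive will be excluded", and the primary exclusion list has "Signs and symptoms of delirium and agitation at time of enrollment (CAM-ICU positive". After enrollment, the secondary exclusions add "signs and symptoms of delirium and agitation at time of study drug initiation (CAM ICU positive".

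**Analysis and planning.** The Delirium paragraph under Exploratory analyses follows the primary and secondary analyses, which are by intention-to-treat. For planning, Delirium in the ICU (B2) says "we expect an incidence of delirium of 28.3"%. Assessment of delirium (B2) says the study is meant to supply effect sizes for later trials.

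**The concern.** The population at risk is fixed at drug initiation, but the outcome clock starts earlier. Suvorexant cannot prevent an episode that is over before the first dose. Under the plain reading of the window and the outcome definition, that episode is still an event. The same kind of episode, if still present at dosing, is a reason for exclusion instead. Its classification therefore depends on whether it has cleared by the evening dose.

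What is at stake is the size of the estimated delirium effect. Events that treatment cannot touch dilute a relative measure and lower power. That matters mainly because the protocol wants this estimate to guide future trials.

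A related gap sits beside it. Randomization follows extubation, so a patient can be randomized and then found CAM-ICU positive at drug initiation. The plan calls this an exclusion and also calls for intention-to-treat, and it does not say which governs the delirium analysis.

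**Working it through.** **1. The plan's own figure.** Sample Size Justification gives 84.4% power for delirium-free days (difference 3, SD 5, 100 patients in total; two-sample t-test, two-sided 0.05). With d = 3/5 = 0.6 and 50 per arm, the noncentral t gives 84.4%. The figure reproduces and is not in dispute.

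**2. Length of the pre-dose interval.** Inputs are the 7 pm cut-off and the 9 to 10 pm dosing window. For an extubation after 7 pm, the first dose is read as falling on the following night.

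- Extubated just before 7 pm: dose the same night, 2 to 3 h later. This is the minimum; an earlier extubation that day gives a longer gap.
- Extubated just after 7 pm: dose the next night, 24 + 2 = 26 h to 24 + 3 = 27 h later.
- Extubated at 10 pm: dose the next night, 23 to 24 h later.

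**3. How an episode in that interval is classified.**

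| Episode | Text that applies | Result |
|---|---|---|
| Present before surgery | Screening Tests; primary exclusions | Excluded |
| Starts after extubation, clears before dosing | Outcome window only | Counts, on the plain reading |
| Starts after extubation, still present at dosing | Secondary exclusion, but intention-to-treat if already randomized | Unresolved if randomized |
| Starts after first dose | Outcome window | Counts |

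**4. Dilution.** Let p be the control incidence counted from extubation and f the share of control-arm cases that are pre-dose. R is the true post-dose risk ratio. From the documents: p = 0.283 and 50 per arm, so 50 × 0.283 = 14.15 control events. Assumed, because the documents give neither: R = 0.50 and f = 5 to 30%. Pre-dose cases are taken to have no later episode.

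- Counting from extubation: control p; suvorexant pf + p(1 − f)R. Observed ratio = f + (1 − f)R.
- Counting from first dose: control p(1 − f); suvorexant p(1 − f)R. Ratio = R.
- Risk difference under both: p(1 − f)(1 − R).

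Example, f = 0.10: suvorexant risk = 0.0283 + 0.2547 × 0.50 = 0.1557. Ratio = 0.10 + 0.90 × 0.50 = 0.55. Risk difference = 0.283 − 0.1557 = 0.1273. Counting from first dose, it is 0.2547 × 0.50 = 0.1273, the same.

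| f | Pre-dose events per 50 controls | Observed ratio | Risk difference | Power, from extubation | Power, from first dose |
|---|---|---|---|---|---|
| 0 | 0 | 0.50 | 0.1415 | 40.8% | 40.8% |
| 5% | 0.71 | 0.53 | 0.1344 | 37.1% | 38.6% |
| 10% | 1.42 | 0.55 | 0.1273 | 33.5% | 36.5% |
| 20% | 2.83 | 0.60 | 0.1132 | 27.0% | 32.4% |
| 30% | 4.24 | 0.65 | 0.0990 | 21.3% | 28.3% |

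Power is for a two-sided 0.05 comparison of two proportions, normal approximation, 50 per arm. The loss runs from 38.6 − 37.1 = 1.5 points to 28.3 − 21.3 = 7.0 points. The 28.3% power in the last row matches the planning incidence only by coincidence. The observed ratio does not depend on p.

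**The case against.** **The text is silent; it does not state a rule.** The window sentence is a general schedule for all exploratory outcomes, and nowhere does the plan define a pre-dose episode as incident delirium. This stands as a limit on the claim. Still, the window, the whole-stay outcome definition and the absence of an onset rule all point the same way.

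**The affected group is narrow.** Patients still positive at drug initiation meet the secondary exclusion, so mainly episodes that start and clear in the interval are affected. If the check at drug initiation serves as the first daily assessment, same-day extubations may contribute none. The 26 to 27 hour gap is a maximum. All of this stands and argues against large shares. It does not close the gap: the protocol describes delirium as fluctuating and the CAM-ICU as routine in the ICU, so a positive result followed by a negative one before dosing is possible.

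**The size is assumed.** It is. Neither the shares nor the halving comes from the documents. The model also leaves out patients with both a pre-dose and a later episode. Including them would not rescue the current window: counted from extubation, such a patient stays a case even if the drug prevents the later episode.

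**The effect is non-differential and the outcome exploratory.** Correct. The plan names no ratio measure for incidence, so the dilution matters only if a relative effect is reported or carried forward.

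**Starting at randomization is an accepted alternative.** It is, and it would also respect intention-to-treat. It would leave the hours between randomization and first dose in the window.

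**Conclusion.** The point holds in a limited form. The delirium window opens before randomization and 2 to 27 hours before the first dose, and no rule covers that interval. On the plain reading, an episode that clears before dosing is an outcome event. Such events are expected equally in both arms. They favour neither arm, and they do not bias the risk difference on the assumption that these patients have no later episode. Extra pre-dose days likewise do not bias the mean difference in delirium-free days. A risk ratio moves toward 1: a true 0.50 would appear as 0.53 to 0.65 for assumed shares of 5 to 30%, with 1.5 to 7 points of power lost. The true share cannot be learned from the documents. WASO, TST and the sample size are untouched.

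Three stronger readings are not supported.

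- A reader might infer that patients need to be delirium-free only at drug initiation. The screening and enrollment exclusions also require it before surgery; what they do not cover is the interval after extubation.
- A reader might infer bias for or against suvorexant. Events before the first dose cannot depend on the allocated drug.
- A reader might infer that 28.3% is an upper value for this population. The documents do not give the eligibility or timing rules of the trial it comes from, and the stated power for delirium rests on delirium-free days.

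**What to change.** In Study design & overview and in the Delirium paragraph under Assessment of study endpoints:

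1. Count incident delirium and delirium-free days from the first scheduled study dose, for all randomized patients. Use the scheduled time rather than actual intake, so that the anchor exists in both arms even when a dose is withheld. Specify the anchor for a randomized patient who leaves the ICU before a first dose.
2. Report positive CAM or CAM-ICU results between extubation and that time as a baseline variable, by arm.
3. State how patients randomized and then found CAM-ICU positive at drug initiation enter the intention-to-treat delirium analysis.

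The 28.3% planning figure can stay as it is. The cost is a few sentences and one date-time filter in the analysis. The downside is slightly fewer counted events: about 0.7 to 4.2 of 14 per control arm under the assumed shares. No treatment or dosing rule changes.
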